7.4 Vital Signs

Descriptive summaries of pre- and post-treatment vital signs including systolic and diastolic blood pressure, pulse, respiratory rate, and body temperature will be prepared for each treatment group by visit.

A listing of all vital sign assessments throughout the study will be provided.

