7.7. Schedule of Study Activities

The schedule of events is presented in [Table 1](#).

Table 1: Schedule of Events

Event	Screening	Dose 1 ^{a,b}	Dose 2, 3 ^a	Follow-up	Follow-up/Early Discontinuation from Study	Study End
	V1	V2	V3, 4	V5	V6	V7
	Day -2 to Day 1	Day 1 ^b	Days 3, 6	Day 10	Day 15	Day 29
Informed consent	X					
Medical history	X					
Pregnancy test ^c	X				X	X
Physical exam	X	X	X	X	X	
Vital signs ^d	X	X	X	X	X	
Pulse oximetry	X					
Spirometry ^e	X	X	X			
Symptom Score	X	X	X	X	X	X
SARS-CoV-2 test ^f	X				X	X
Ordinal Scale for Clinical Improvement	X	X	X	X	X	X
Study drug administration ^g		X	X			
Adverse events	X	X	X	X	X	X
Concomitant medications	X	X	X	X	X	X
Randomization	X					

^a Vital signs, adverse events, and concomitant medications will be assessed prior to administration of study medication and also at 30 minutes post-dose.

^b There is no Day 0 in this study

^c Urine pregnancy test or serum pregnancy test if women are of child-bearing potential. If urine pregnancy test is positive, a serum pregnancy test must be done. Pregnancy test will be repeated at Day 29 or Early Discontinuation

^d Vital signs will include body temperature, blood pressure measurements, heart rate, and respiratory rate

^e Spirometry will be done at screening to document eligibility. On days of dosing, spirometry will be done pre-dose and at 30 minutes (± 15) minutes post-dose. If the FEV1 is reduced $> 10\%$ compared to the pre-dose baseline the FEV1 should be repeated as clinically indicated

^f SARS-CoV-2 testing will be performed at screening to confirm eligibility if a positive test SARS-CoV-2 has not been documented. SARS-CoV-2 testing will be performed at Early Discontinuation visit

^g Study drug administration must be done by a health care professional

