7.14. Early Discontinuation from Dosing and Study Withdrawal

Subjects who have received at least one dose of investigational treatment and are discontinued from dosing should continue to the final assessment at Day 29 according to the schedule of events specified for pre-dose assessments. There will be no post-dose assessments for these subjects.

Should the subject's study participation end prior to the completion of Study Day 15, the following assessments will be conducted as soon as possible after the decision to withdraw from the study is made.

- Serum pregnancy test or urine test (if urine positive, a serum test must be conducted)
- Physical examination
- Vital signs
- Nasopharyngeal or oropharyngeal sample for SARS-CoV-2 testing
- SARS- CoV-2 infection symptom score
- Ordinal Scale for Clinical Improvement assessment
- Adverse event assessment
- Concomitant medication assessment

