2.2.3 Safety and Tolerability Endpoints

- Change in forced expiratory volume in 1 second (FEV1) from Pre-dose to Post-dose
- Treatment-emergent serious adverse events (SAEs) through Day 29
- Treatment-emergent adverse events (TEAEs) and severity through Day 29
- Vital signs from Pre-dose to Post-dose

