4. GENERAL CONSIDERATIONS FOR DATA ANALYSIS

Unless otherwise specified, continuous variables will be summarized using descriptive statistics

(n, mean, standard deviation, median, minimum, and maximum). Categorical variables will be summarized showing the number and percentage of subjects within each category.

Summary results will be provided for each treatment group. All tabulations will be based on pooled data across centers.

Unscheduled visits will be excluded from the summaries but will be included in the data listings.

All statistical tests will be two-sided and tested at the 5% level of significance.

Analyses will be performed using SAS for Windows statistical software, version 9.4 or higher (SAS, Cary, NC), except where other software may be deemed more appropriate.

CTI will perform all efficacy and safety analyses described in this SAP.

Subject data will be listed, sorted by treatment group and subject number. When applicable, listings will be additionally sorted by visit and assessment date/time.

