7.3 Pulmonary Function Testing

Spirometry tests including FEV1 (L), % predicted FEV1, FVC (L), % predicted FVC and FEV1/FVC values will be collected at screening and FEV1 (L) will also be recorded at the time points presented in the Appendix A. FEV1 results will be summarized by presenting descriptive statistics of raw data of FEV1 (L) and percent change from each Pre-dose value to Post-dose value on the dosing days.

The proportion of subjects with percent decrease in FEV1 (L) from Pre-dose value to Post-dose value will be presented for each category: >10% and <=12% of reduction; >12% and <=20% of reduction; and >20% of reduction at each measurement time point (Day1, Day 3 and Day 6).

The percent change in FEV1 (L) from Pre-dose value to the protocol defined 30-min Post-dose values will be illustrated in a box/whisker graph on each dosing day by treatment group.

Spirometry results from unscheduled visits will be excluded from table summaries but will be included in the data listing.

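### Vital signs: SAP 7.4 specifies no same-day within-subject change, and on Days 3 and 6 the post-dose row can cover only a subset of the pre-dose row

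*SAP*

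**What the plan says.** SAP 2.2.3 lists among the safety endpoints "Vital signs from Pre-dose to Post-dose". The only analysis text for it is SAP 7.4: "Descriptive summaries of pre- and post-treatment vital signs including systolic and diastolic blood pressure, pulse, respiratory rate" and body temperature, for each arm and visit, plus a full listing. The default statistics in SAP 4 are "n, mean, standard deviation, median, minimum, and maximum". No change score is named, and nothing limits the rows to subjects with both values. For FEV1, by contrast, SAP 7.3 specifies "percent change from each Pre-dose value to Post-dose value on the dosing days".

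On timing, footnote a to the schedule in Protocol 7.7 states: "Vital signs, adverse events, and concomitant medications will be assessed prior to administration of study medication and also at 30 minutes post-dose". Protocol 7.11.1 and 7.11.3 put vital signs in both the pre-dose and the 30-minute lists for Days 3 and 6.

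For subjects who have had at least one dose and stop dosing, Protocol 7.14 says that they "should continue to the final assessment at Day 29 according to the schedule of events specified for pre-dose assessments", and then: "There will be no post-dose assessments for these subjects". Protocol 11.2 repeats the rule. SAP 4.3 groups data by nominal visit, and SAP 4.4 leaves missing vital signs missing.

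**The concern.** A reader of the SAP 7.4 table will compare the pre-dose and post-dose rows to see what happens to pulse, respiratory rate, blood pressure and temperature shortly after inhalation. That comparison is sound only if both rows hold the same subjects. On Days 3 and 6 the Protocol gives a reason why they may not: subjects already off drug supply a value at the pre-dose time and none at the post-dose time.

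These subjects are not a random sample. Protocol 7.10.2, 7.11.1 and 7.11.2 allow dosing to end for FEV1 falls, for safety, or because COVID-19 has worsened. A subject whose disease is worsening may well have a raised pulse, respiratory rate or temperature. Including such subjects in the first row and not in the second pulls the apparent change downward, so a small post-dose rise could go unseen.

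**Working it through.** The plan gives no figure for vital signs, so there is nothing to reproduce. The check is the algebra of two row means.

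**Inputs from the documents.** About 50 subjects per arm (Protocol 7.4). Off-drug subjects are on the pre-dose schedule with no post-dose values (Protocol 7.14, 11.2).

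**Inputs assumed, because the documents give none.** f is the share of an arm's pre-dose row that is off drug, taken as 4–20% (2 to 10 of 50). d is the pre-dose mean of off-drug subjects minus that of dosed subjects, taken as 5–10 breaths/min for respiratory rate. δ is the true mean change in dosed subjects.

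**Formula.** Let m be the pre-dose mean in dosed subjects.
- Pre-dose row: (1 − f) × m + f × (m + d) = m + f × d
- Post-dose row: m + δ
- Difference between rows: δ − f × d

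The distortion is therefore −f × d, and the change is masked completely when f × d = δ.

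**Respiratory rate, −f × d.**
- 2 of 50 off drug (4%): −0.2 at d = 5, −0.4 at d = 10
- 5 of 50 (10%): −0.5 and −1.0
- 10 of 50 (20%): −1.0 and −2.0

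**Worked case (assumed).** 45 dosed subjects at 18 breaths/min, 5 off drug at 28, true rise 1.
- Pre-dose row: (45 × 18 + 5 × 28) / 50 = 950 / 50 = 19.0
- Post-dose row: 18 + 1 = 19.0
- Apparent change: 0. Paired change in the 45 dosed: 19 − 18 = +1.

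**How many must stop to mask a change.** The number out of 50 is 50 × δ / d. For δ = 1 it is 10 at d = 5 and 5 at d = 10. For δ = 2 it is 20 and 10.

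**Day 1.** SAP 4.2 admits to both analysis sets only subjects who received at least one dose, so nobody in the Day 1 table is off drug beforehand. There f = 0 and the distortion is zero.

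**The case against.** The strongest reply is that this argues from silence. SAP 7.4 does not say that the summaries are separate and does not exclude a change row. The from-and-to wording in SAP 2.2.3 may intend one, and table shells are not part of the documents. It is also not stated that a value from an untreated visit would be placed in a pre-treatment row; that is the likely reading of Protocol 7.14 with SAP 4.3, but only a reading. This stands to the extent that the SAP should be described as not specifying a paired change rather than as ruling one out. It does not remove the gap: SAP 7.3 spells out the change for FEV1, and SAP 7.4 does not for vital signs.

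A second reply is that other outputs limit the harm. Row counts would show the mismatch, SAP 7.1 tabulates doses received and reasons for stopping, the listing would allow a paired calculation, and the acute airway effect is read mainly from the paired FEV1 analysis. All of that is right, and it keeps the point minor.

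Four stronger inferences are tempting, and the documents do not support them:
- *The two rows describe different subjects.* Stray missing values aside, the post-dose row is a subset of the pre-dose row; in the worked case 45 of 50 subjects are common to both.
- *The distortion is larger on PUL-042.* The only documented reason to expect more stops on PUL-042 is the FEV1 fall seen in phase 1 (Protocol 5.4). Those falls were short-lived and came without respiratory distress or desaturation (Protocol 5.4), and Protocol 7.10.2 describes them as mostly symptomless. At a later visit d could be near zero for such subjects. A large d is plausible for deterioration stops, but nothing suggests that these are commoner on PUL-042.
- *The precision of the change is misstated.* No standard error of change is planned, and SAP 7 rules out formal tests between arms for safety.
- *The sign will reverse.* The algebra allows it when f × d exceeds δ, but only with assumed values. In an assumed pulse grid (d of 5–20 bpm, true rise of 1–3 bpm), no case reverses with 2 of 50 off drug; the distortion there is −0.2 to −0.8 bpm.

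**Conclusion.** The point holds as a minor improvement. SAP 7.4 does not specify the within-subject change that its own endpoint wording points to. On Days 3 and 6 the difference between its two row means equals the true change minus f × d. Under assumed f of 4–20% and d of 5–10 breaths/min, this is a distortion of −0.2 to −2.0 breaths/min: negligible if few subjects stop, enough to mask a small change if many deteriorating subjects stop.

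The size rests wholly on assumed values of f and d, and on off-drug values entering the pre-dose row. The sign rests on off-drug subjects having the higher values. Day 1 is unaffected. The table is descriptive and bears on neither the efficacy analyses nor the mortality stopping rule.

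**What to change.** In SAP 7.4, add the within-subject change from the same-day pre-dose value to the 30-minute post-dose value on Days 1, 3 and 6, by arm, in subjects dosed at that visit who have both values, with n shown. Present the pre-dose and post-dose rows for those same subjects. Summarise the vital signs of subjects not dosed at that visit in a separate row, and keep the listing.

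The paired change returns δ whatever f and d are, and it brings SAP 7.4 into line with SAP 2.2.3 and 7.3. The cost is a sentence or two in the SAP and one revised table shell, with no new data. The only downside is one extra row per visit.

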7.5 Other Safety Measures

Pregnancy test results, if applicable, will be presented in a listing.

8. INTERIM ANALYSES

An external DSMB will be used to evaluate safety of the study in an ongoing manner. A full description of the membership, role, and responsibilities of the DSMB is provided in the DSMB charter. As specified in the DSMB charter, the formal review of data will take place at each meeting of the DSMB after 20, 40 and 60 subjects have completed dosing.

As a further effort to ensure the safety of PUL-042, a stopping rule that is based only on mortality will be employed. A recommendation to stop the study would be made only if there is a high probability of excess mortality risk among subjects randomized to PUL-042. The following hierarchical analysis of mortality will be performed after 50% of subjects have been enrolled (25/group) and followed up for 28 days from the start of investigational therapy:

- 1) Based on blinded data, if no more than 1 death has occurred during the study this analysis will not be conducted due to the lack of evidence of increased mortality risk attributable to PUL-042.

If more than 1 death occurs:

- 2) The Unblinded statistician will evaluate unblinded mortality data to determine the treatment specific death rate (i.e., $D_{Tx} = \text{Deaths}_{Tx} / N_{Tx}$; $Tx = \text{Active or Placebo}$).
- 3) If the difference, Δ , in treatment-specific death rates (i.e., $\Delta = D_{\text{Active}} - D_{\text{Placebo}}$) is greater than 7.5%, the DSMB will further review the totality of evidence and render a recommendation to the sponsor regarding study continuation.

Characteristics of this rule are as follows:

Assuming that the true underlying control arm mortality rate is 5% and using a normal approximation when comparing proportions, the probability of stopping is approximately:

- 90% if the true underlying mortality rate attributable to PUL-042 is 25%.
- 62% if the true underlying mortality rate attributable to PUL-042 is 15%.
- only 11% if the true underlying mortality rate attributable to PUL-042 is 5% (equal to the assumed true underlying control arm mortality rate).

9. SAMPLE SIZE AND POWER CALCULATIONS

The trial size of 100 subjects (50 PUL-042 inhalation solution: 50 placebo) was chosen based on clinical considerations. The rates of infection to adequately estimate a sample size for a statistically significant result are unknown.

Enrolled subjects will be randomized with equal probability to receive blinded treatment consisting of either PUL-042 or placebo.

11. APPENDIX

11.1 Appendix A: Schedule of Events

Event	Screening	Dose 1 ^{a,b}	Dose 2, 3 ^a	Follow-up	Follow-up/Early Discontinuation from Study	Study End
	V1	V2	V3, 4	V5	V6	V7
	Day -2 to Day 1	Day 1 ^b	Days 3, 6	Day 10	Day 15	Day 29
Informed consent	X					
Medical history	X					
Pregnancy test ^c	X				X	X
Physical exam	X	X	X	X	X	
Vital signs ^d	X	X	X	X	X	
Pulse oximetry	X					
Spirometry ^e	X	X	X			
Symptom Score	X	X	X	X	X	X
SARS-CoV-2 test ^f	X				X	X
Ordinal Scale for Clinical Improvement	X	X	X	X	X	X
Study drug administration ^g		X	X			
Adverse events	X	X	X	X	X	X
Concomitant medications	X	X	X	X	X	X
Randomization	X					

^a Vital signs, adverse events, and concomitant medications will be assessed prior to administration of study medication and also at 30 minutes post-dose.

^b There is no Day 0 in this study

^c Urine pregnancy test or serum pregnancy test if women are of child-bearing potential. If urine pregnancy test is positive, a serum pregnancy test must be done.

Pregnancy test will be repeated at Day 29 or Early Discontinuation

^d Vital signs will include body temperature, blood pressure measurements, heart rate, and respiratory rate

^e Spirometry will be done at screening to document eligibility. On days of dosing, spirometry will be done pre-dose and at 30 minutes (± 15) minutes post-dose. If the FEV1 is reduced $> 10\%$ compared to the pre-dose baseline the FEV1 should be repeated as clinically indicated

^f SARS-CoV-2 testing will be performed at screening to confirm eligibility if a positive test SARS-CoV-2 has not been documented. SARS-CoV-2 testing will be performed at Early Discontinuation visit

^g Study drug administration must be done by a health care professional
